1 GLOSSARY OF TERMS

Names of test product(s)	Throughout this document, test product(s) will be referred to as [REDACTED] soft contact lenses or [REDACTED] contact lenses [REDACTED]
Name of Control Product(s)	CooperVision® BIOFINITY® (comfilcon A) soft contact lenses (Biofinity contact lenses or Biofinity)
Adverse Device Effect (ADE)	Adverse event related to the use of an investigational medical device (test product) or control product. Note: This definition includes adverse events resulting from insufficient or inadequate instructions for use, deployment, implantation, installation, or operation; any malfunction; and use error or intentional misuse of the test product or control product.
Adverse Event (AE)	Any untoward medical occurrence, unintended disease or injury, or untoward clinical signs (including abnormal laboratory findings) in subjects, users or other persons, whether or not related to the investigational medical device (test product). Note: For subjects, this definition includes events related to the test product, the control product, or the procedures involved. For users or other persons, this definition is restricted to events related to the test product. Requirements for reporting Adverse Events in the study can be found in Section 11.
Anticipated Serious Adverse Device Effect	Serious adverse device effect which by its nature, incidence, severity, or outcome has been identified in the risk management file.
Device Deficiency	Inadequacy of a medical device with respect to its identity, quality, durability, reliability, safety, or performance. Note: This definition includes malfunctions, use errors, and inadequate labeling.

	Requirements for reporting Device Deficiencies in the study can be found in Section 11.
Enrolled Subject	Any subject who signs an informed consent form for participation in the study.
Interventional Clinical Trial	A research trial that prospectively assigns, whether randomly or not, human participants or groups of humans to one or more health-related interventions to evaluate the effects on health outcomes, and/or a research trial in which diagnostic or monitoring procedures beyond standard of care are conducted and generate outcomes for use in analysis of data.
Investigational Product (IP)	Is defined as a preventative (vaccine), a therapeutic (drug or biologic), device, diagnostic, or palliative used as a test or control product in a clinical trial, including a product with a marketing authorization when used or assembled (formulated or packaged) in a way different from the authorized form, or when used for an unauthorized indication, or when used to gain further information about the authorized form.
Malfunction	Failure of a medical device to perform in accordance with its intended purpose when used in accordance with the instructions for use or clinical investigation plan.
Non-serious Adverse Event	Adverse event that does not meet the criteria for a serious adverse event.
Randomized Subjects	Any subject who is assigned a randomized treatment.
Serious Adverse Device Effect (SADE)	Adverse device effect that has resulted in any of the consequences characteristic of a serious adverse event.
Serious Adverse Event (SAE)	Adverse event that led to any of the following: 
 • Death.

	
• A serious deterioration in the health of the subject that either resulted in:
a. a life-threatening illness or injury. Note: Life-threatening means that the individual was at immediate risk of death from the event as it occurred, ie, it does not include an event which hypothetically might have caused death had it occurred in a more severe form.b. any potentially sight-threatening event or permanent impairment to a body structure or a body function.c. in-patient hospitalization or prolonged hospitalization. Note: Planned hospitalization for a pre-existing condition, without serious deterioration in health, is not considered a serious adverse event. In general, hospitalization signifies that the individual remained at the hospital or emergency ward for observation and/or treatment (usually involving an overnight stay) that would not have been appropriate in the physician's office or an out-patient setting. Complications that occur during hospitalization are adverse events. If a complication prolongs hospitalization or fulfills any other serious criteria, the event is serious. When in doubt as to whether "hospitalization" occurred, the event should be considered serious.d. a medical or surgical intervention to prevent a) or b).e. any indirect harm as a consequence of incorrect diagnostic test results when used within manufacturer's instructions for use.
--	---

	
• Fetal distress, fetal death, or a congenital abnormality or birth defect. 
Refer to Section 11 for additional SAEs.

Significant Non-Serious Adverse Event	
Is a symptomatic, device-related, non-sight threatening adverse event that warrants discontinuation of any contact lens wear for greater than or equal to 2 weeks.
 
Refer to Section 11 for additional Significant Non-Serious AEs.

Unanticipated Serious Adverse Device Effect	Serious adverse device effect which by its nature, incidence, severity or outcome has not been identified in the risk management file.
Use Error	Act or omission of an act that results in a different medical device response than intended by manufacturer or expected by user. Note: This definition includes slips, lapses, and mistakes. An unexpected physiological response of the subject does not in itself constitute a use error.

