11 ADVERSE EVENTS AND DEVICE DEFICIENCIES

11.1 General Information

An AE is any untoward medical occurrence, unintended disease or injury, or untoward clinical signs (including abnormal laboratory findings) in subjects, users, or other persons, whether or not related to the investigational medical device (test article). Refer to the Glossary of Terms and figures below for categories of AEs and SAEs.

Figure 11-1 Categorization of All AEs

[figure not shown]
[figure not shown]

Figure 11-2 Categorization of All SAE

SAEs

In addition to reporting all AEs (serious and non-serious) meeting the definitions, the Investigator must report any occurrence of the following as an SAE:

- An ocular infection including a presumed infectious ulcer with any of the following characteristics*:
 - Central or paracentral location
 - Penetration of Bowman's membrane
 - Infiltrates > 2 mm diameter
 - Iritis
 - Increase in intraocular pressure
 - Culture positive for microorganisms
 - Increasing size or severity at subsequent visits
- Any central or paracentral corneal event (such as neovascularization) that results in permanent opacification

- Hypopyon
- Hyphema
- Neovascularization within the central 6 mm of the cornea
- Permanent vision loss as defined by loss of 2 or more lines of BCVA from enrollment visit that fails to resolve
- Uveitis (anterior, intermediate, or posterior)
- Corneal abrasion affecting \geq 50% of corneal surface area

Significant Non-Serious AE

A significant non-serious AE is a device-related, non-sight threatening AE that warrants discontinuation of any contact lens wear for greater than or equal to 2 weeks. In addition, the Investigator must report any occurrence of the following as a Significant Non-Serious Adverse Event:

- Peripheral non-progressive non-infectious ulcers
- All symptomatic corneal infiltrative events
- Corneal staining score greater than or equal to Grade 3 [REDACTED]
[REDACTED]
- Temporary vision loss as defined by loss of 2 or more lines of BCVA from enrollment visit that persists for 2 or more weeks
- Neovascularization score greater than or equal to Grade 2 [REDACTED]
[REDACTED]

Device Deficiencies

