12.6 Safety Analyses

The safety endpoints are:

- AEs
- Biomicroscopy Findings
- Device Deficiencies

There are no safety hypotheses planned in this study. The focus of the safety analysis will be a comprehensive descriptive assessment of occurrence of AE as well as the other listed parameters.

All AEs occurring from the time a subject signs informed consent to study exit will be accounted for in the reporting. Safety analyses will be conducted using the safety analysis set on a treatment-emergent basis. Descriptive summaries (counts and percentages) for ocular and nonocular AEs will be presented by Medical Dictionary for Regulatory Activities Preferred Terms. AEs leading to study discontinuation, significant non-serious AEs, and SAEs will be identified. Individual subject listings will be provided, as necessary.

Individual subject listings will be provided for AEs that occur after signing informed consent but prior to exposure to IP.

Two listings for device deficiencies, prior to exposure of study contact lenses and treatment-emergent, will be provided. Additionally, each device deficiency category will be tabulated.

No inferential testing will be done for safety analysis.

[REDACTED]

[REDACTED]

[REDACTED]

[REDACTED]

[REDACTED]

[REDACTED]

[REDACTED]

[REDACTED]

| [REDACTED]

| [REDACTED]

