## 5.3 Statistical Methods for Safety Analyses

### 5.3.1 Adverse Events

[figure not shown]
The applicable definition of an AE is in the study protocol. All AEs occurring from when a subject signs informed consent to when a subject exits the study will be accounted for in the reporting. Analysis and presentation of pre-treatment AEs will be separated from treatment-emergent AEs occurring during the study period. A pre-treatment AE is an event that occurs after signing informed consent but prior to exposure to study lenses (not including trial fitting lenses). The period for treatment-emergent AE analysis starts from exposure to study lenses until the subject completes or is discontinued from the study.

Descriptive summaries (counts and percentages) for ocular and nonocular AEs will be presented by Medical Dictionary for Regulatory Activities (MedDRA) Preferred Terms (PT). Serious AEs and significant non-serious ocular AEs will be noted. Additionally, relationship to lens will be identified in all AE tables. Unit of presentation for ocular AEs will be eye and nonocular AEs will be subject.

Individual subject listings will be provided for both pre-treatment and treatment-emergent AEs, where any AE leading to study discontinuation will be indicated.

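### Does it matter that the Glossary limits Significant Non-Serious AEs to symptomatic events while protocol Section 11.1 does not?

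*Protocol*

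**What the plan says.** The category is defined twice in the protocol.

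- Section 1 (Glossary): "Is a symptomatic, device-related, non-sight threatening adverse event that warrants discontinuation of any contact lens wear", with a duration of two weeks or more. The entry ends "Refer to Section 11 for additional Significant Non-Serious AEs".
- Section 11.1: "A significant non-serious AE is a device-related, non-sight threatening AE that warrants discontinuation of any contact lens wear", with the same duration. It continues "In addition, the Investigator must report any occurrence of the following as a Significant Non-Serious Adverse Event" and names five event types. One of them is "All symptomatic corneal infiltrative events"; the others are certain peripheral ulcers, corneal staining of Grade 3 or more, a defined temporary vision loss, and neovascularization of Grade 2 or more.

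The opening of Section 11.1 sends the reader back: "Refer to the Glossary of Terms and figures below for categories of AEs and SAEs".

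Both documents then use the category. Protocol Section 12.6: "AEs leading to study discontinuation, significant non-serious AEs, and SAEs will be identified". SAP Section 5.3.1: "Serious AEs and significant non-serious ocular AEs will be noted". The visible SAP text does not define the category itself; for what counts as an AE it defers to the protocol.

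**The concern.** Two definitions of one safety category differ in a condition for membership, and each section refers to the other without saying which governs. The protocol elsewhere treats symptoms as a real dividing line, since the infiltrative-event item on the Section 11.1 list is confined to symptomatic cases while the staining and neovascularization items are not. Biomicroscopy is scheduled at every visit and the AE definition covers clinical signs, so an asymptomatic finding can come to light.

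With about 16 sites, the same finding could then be flagged at one site and not at another. Safety is assessed descriptively, so categories and tabulations are all the safety output there is, and an inconsistently applied category would be harder to read. If the flag decided whether an event was captured or shown at all, this would be worth correcting now.

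**Working it through.** No figure in the plan depends on this wording, so the check is a comparison of the texts.

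**Step 1. Compare the two general definitions.**

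| Element | Glossary | Section 11.1 |
|---|---|---|
| Symptomatic | required | not mentioned |
| Device-related | required | required |
| Not sight-threatening | required | required |
| Two weeks or more out of lenses | required | required |

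**Step 2. Find which events are classified differently.** Take an event that meets the three shared elements.

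- Symptomatic: in the class under both texts.
- Asymptomatic and on the Section 11.1 list: in the class under both, because the list adds to the general definition.
- Asymptomatic and not on the list: in the class under Section 11.1, outside it under the Glossary.

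Only the third case is affected. An example is an asymptomatic infiltrative event that meets the three shared elements and matches no other listed item.

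**Step 3. Follow such an event through the plan.** It is device-related, so it is an adverse device effect.

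- Protocol Section 11.3 puts it on the Serious Adverse Event and Adverse Device Effect eCRF within 24 hours of the site's awareness, with severity, treatment, outcome, seriousness and causality. The flag plays no part in this.
- SAP Section 5.3.1 counts it under its Preferred Term, shows its relationship to the lens in every AE table, and includes it in the individual listings, which also mark any AE that led to study discontinuation.

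The event appears in all of these places under either definition. Only the mark for this category differs.

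**Step 4. Ask what number could move.** Protocol Section 12.6 says the category will be identified, and SAP Section 5.3.1 says it will be noted. The counts and percentages that are specified are by Preferred Term. If a rate for the class were nevertheless calculated, and all planned randomized subjects wore lenses in both eyes, the denominators would be 96 × 2 = 192 test eyes and 48 × 2 = 96 control eyes. One eye would then be 1/192 = 0.52% or 1/96 = 1.04%. That is simply what any single eye contributes. It says nothing about how often the disputed case will arise, and the documents give no basis for estimating that.

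**Step 5. Check for inference.** Protocol Section 12.6 rules out inferential testing of safety. The visual acuity endpoints do not use AE categories.

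**The case for a change.** The best argument for acting now is that the contradiction is certain and cheap to remove. The visible text does not settle it: the Glossary's pointer to Section 11 most naturally refers to the added list, and Section 11.1 points back to the Glossary. For serious AEs, Section 11.1 adds a list and leaves the base definition in the Glossary; for this category it restates the base definition and changes it. In a descriptive safety report, consistent labels matter.

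The wording conflict stands in full. The claim that sites will diverge is weaker. The Glossary's AE entry and Section 10.2.4 both direct sites to Section 11 for reporting requirements, so sites are likely to work from one text, although this is not a precedence clause. Figure 11-1, to which Section 11.1 refers for AE categories, is not available here, and parts of Section 11 are redacted, so the absence of a resolving rule is established only for the visible text. The claim that a category count would be distorted does not stand, because no visible text promises one.

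**Conclusion.** This is a clerical slip: one condition appears in one statement of a definition and not in the other. Its reach is a single descriptive flag on an asymptomatic, unlisted, device-related event that still calls for two weeks or more without lenses. Recording, 24-hour entry, tabulation by Preferred Term, attribution to the lens and individual listing are the same under both wordings. Reconciling them would improve no estimate, precision, bias or conclusion, and no visible protection of subjects depends on the flag.

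The two passages do contradict each other and must be reconciled, but that is routine housekeeping for the next protocol revision. The choice of wording belongs to the sponsor. The SAP needs no edit, since it takes its AE definition from the protocol. The item on symptomatic infiltrative events fits either general definition and does not need revisiting.

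The conclusion rests on two assumptions: that the redacted parts of Section 11 attach no separate action to this flag, and that no output gives a rate for the class. Nothing visible contradicts either.

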2 LIST OF ACRONYMS AND ABBREVIATIONS

Table 2-1

List of Acronyms and Abbreviations Used in This Protocol

Abbreviation	Definition
ADE	Adverse device effect
AE	Adverse event
[REDACTED]	[REDACTED]
Biofinity contact lens or Biofinity	CooperVision BIOFINITY (comfilcon A) soft contact lenses (LID010221)
CFR	Code of Federal Regulations
CI	Confidence interval
CLCDVA	Contact lens corrected distance visual acuity
CLEAR CARE	CLEAR CARE® Cleaning & Disinfecting Solution
[REDACTED]	[REDACTED]
CRF	Case report form
[REDACTED]	[REDACTED]
D	Diopter(s)
D/C	Discontinue
[REDACTED]	[REDACTED]
eCRF	Electronic case report form
EDC	Electronic data capture
FAS	Full analysis set
FDA	US Food and Drug Administration
GCP	Good Clinical Practice
IB	Investigator's brochure
ICF	Informed consent form
[REDACTED]	[REDACTED]
IEC	Independent ethics committee
[REDACTED]	[REDACTED]
IP	Investigational product
IRB	Institutional review board
ISO	International Organization for Standardization
[REDACTED]	[REDACTED]
LID	Lens identification
logMAR	Logarithm of the minimum angle of resolution
[REDACTED] contact	[REDACTED] soft contact lenses (LID018869)
lens or [REDACTED]	[REDACTED]
[REDACTED]	[REDACTED]
N/A	Not applicable
OD	Right eye

Abbreviation	Definition
OS	Left eye
OU	Both eyes
[REDACTED]	[REDACTED]
PP	Per protocol analysis set
SADE	Serious adverse device effect
SAE	Serious adverse event
SD	Standard deviation
SiHy	Silicone hydrogel
SOP	Standard operating procedure
[REDACTED]	[REDACTED]
UCDVA	Uncorrected distance visual acuity
US / USA	United States of America
USV	Unscheduled visit
VA	Visual acuity
vs	Versus

3 PROTOCOL SUMMARY

This will be a prospective, randomized, [REDACTED] controlled, double-masked, parallel-group daily wear clinical study.

Approximately 16 sites in the US will enroll approximately 160 subjects. Subjects will be expected to attend 4 office visits: Screening/Baseline/Dispense, Week 1 Follow-up, Month 1 Follow-up, and Month 3 Follow-up/Exit. The total expected duration of participation for each subject is approximately 3-4 months in this daily wear clinical study. Accounting for both screen failure and dropout rates, approximately 96 subjects will be assigned to wear the test lenses and 48 subjects will be assigned to wear the control lenses, [REDACTED]

[REDACTED]
[REDACTED].

[REDACTED]
[REDACTED]
[REDACTED]
[REDACTED]
[REDACTED].

Subjects and the study personnel conducting the study evaluations will be masked to treatment. Subjects who meet the inclusion and exclusion criteria will be randomized to wear either the test contact lenses [REDACTED] in both eyes or the control contact lenses (Biofinity) in both eyes for 3 months of daily wear exposure.

[REDACTED]
[REDACTED]
[REDACTED]
[REDACTED]
[REDACTED]
[REDACTED]
[REDACTED]
[REDACTED].

At the Screening/Baseline/Dispense Visit, study lenses will be dispensed to qualified subjects [REDACTED]

[REDACTED] All study lenses will be worn for at least 5 days per week and 8 hours per day in a daily wear modality (eg, will not be worn while sleeping). [REDACTED]

[REDACTED]

[REDACTED]

[REDACTED]. Regardless of whether the subject is randomized to the test or the control group, CLEAR CARE Cleaning & Disinfecting Solution (CLEAR CARE) must be used for cleaning and disinfection. [REDACTED]

Investigational product type	Medical Device
Study type	Interventional
Investigational products	Test Product: [REDACTED] soft contact lens Control Product: Biofinity soft contact lens
Purpose and rationale	The purpose of this clinical study is to evaluate the safety and performance of the investigational [REDACTED] soft contact lens compared to the commercially available Biofinity soft contact lens, when worn in a daily wear modality, by assessing visual acuity as the primary endpoint.

	
■ [REDACTED]
 
Safety
 
 • AEs • Biomicroscopy • Device deficiencies
Study Design	
This will be a prospective, randomized, [REDACTED] controlled, double-masked, parallel-group, daily wear clinical study. Subject participation in the study will be approximately 3 – 4 months with approximately 3 months of exposure to study lenses.

Subject population	
Volunteer subjects aged 18 or over who are adapted daily wear frequent replacement soft contact lens wearers, excluding Biofinity habitual wearers, have at least 3 months of soft contact lens wearing experience, and who wear their habitual lenses at least 5 days per week and at least 8 hours per day.
 
[REDACTED]
 
[REDACTED]

Key inclusion criteria (See Section 8.1 for a complete list of inclusion criteria)	
 • Successful wear of spherical daily wear frequent replacement soft contact lenses for distance correction in both eyes during the past 3 months for a minimum of 5 days per week and 8 hours per day • Manifest cylinder ≤ 0.75 D in each eye

	
 Best spectacle corrected visual acuity (using manifest refraction) of 20/20 or better in each eye 
[REDACTED]
 
[REDACTED]
															
Key exclusion criteria (See Section 8.2 for a complete list of exclusion criteria)	
 Wearing habitual contact lenses in an extended wear modality (routinely sleeping in lenses for at least 1 night per week) over the last 3 months prior to enrollment Monovision or multifocal contact lens wearers Habitually wearing Biofinity lenses 															
Data analysis 
[REDACTED]
 
[REDACTED]
	
To address the primary and secondary effectiveness objectives, data from a pre-determined subset of subjects (see Section 12) from CLY935-C010 will be combined with the current study, and all planned analyses will be performed on this combined set as summarized below:
 
  
 Endpoint	Comparison	Statistical Method	
   
 Primary	[REDACTED] vs Biofinity	Mixed effects	
 
 Mean CLCDVA (Week 1 Follow-up)	Noninferiority (margin = 0.10 logMAR)	repeated measures model	
 
 Secondary	[REDACTED] vs Biofinity	Generalized linear	
 
 Proportion of subjects with CLCDVA of 20/20 or better in both eyes (Week 1 Follow-up)	Noninferiority (margin = 0.10)	mixed model	
  
 
[REDACTED]
 
[REDACTED]
 
[REDACTED]
 
No inferential testing will be carried out for safety endpoints.
	Endpoint	Comparison	Statistical Method	Primary	[REDACTED] vs Biofinity	Mixed effects	Mean CLCDVA (Week 1 Follow-up)	Noninferiority (margin = 0.10 logMAR)	repeated measures model	Secondary	[REDACTED] vs Biofinity	Generalized linear	Proportion of subjects with CLCDVA of 20/20 or better in both eyes (Week 1 Follow-up)	Noninferiority (margin = 0.10)	mixed model
Endpoint	Comparison	Statistical Method														
Primary	[REDACTED] vs Biofinity	Mixed effects														
Mean CLCDVA (Week 1 Follow-up)	Noninferiority (margin = 0.10 logMAR)	repeated measures model														
Secondary	[REDACTED] vs Biofinity	Generalized linear														
Proportion of subjects with CLCDVA of 20/20 or better in both eyes (Week 1 Follow-up)	Noninferiority (margin = 0.10)	mixed model														

Table 3-1 Schedule of Study Procedures and Assessments

Procedure/ Assessment	Visit 1 Screening/ Baseline/ Dispense	Visit 2 Week 1 Follow-up ⁵	Visit 3 Month 1 Follow-up ⁵	Visit 4 Month 3 Follow-up/Exit ⁵	Early Exit	USV
	Day 1	Day 8	Day 30	Day 95		
Informed Consent	X					
Demographics	X					
Medical History	X	X	X	X	X	(X)
Pregnancy	X	X	X	X	X	(X)
Concomitant Medications	X	X	X	X	X	(X)
Inclusion/Exclusion	X					
Habitual lens information (brand/manufacturer, power, modality/wear success, habitual lens care brand)	X					
		X			X	
		X			X	
		X	X		X	
		X	X		X	
		X			X	
Biomicroscopy	X	X	X	X	X	(X)
		X			X	
		X			X	
		X			X	
Randomize and record lens power	X					

[figure not shown]
Printed By:

Print Date:

Printed By:

Print Date:

Procedure/ Assessment	Visit 1 Screening/ Baseline/ Dispense	Visit 2 Week 1 Follow-up ⁵	Visit 3 Month 1 Follow-up ⁵	Visit 4 Month 3 Follow-up/Exit ⁵	Early Exit	USV
	Day 1	Day 8	Day 30	Day 95		
		■	■	■	■	■
		■	■	■	■	■
		■	■	■	■	■
Adverse Events	X	X	X	X	X	(X)
Device deficiencies	X	X	X	X	X	(X)
Exit Form	(X)	(X)	(X)	X	X	(X)

